1.1. Responsibilities

Syneos Health will perform the statistical analyses and is responsible for the production and quality control of all SDTMs, derived datasets, and tables, listings, and figures (TLFs).

1.2. Timing of Analyses

The primary analysis of safety and efficacy and/or pharmacodynamics is planned after all subjects complete the final study visit or terminate early from the study. Unless otherwise specified, the analysis includes all data collected in the database through the time of the database lock.

2. Study Objectives and Endpoints

2.1. Study Objectives

2.1.1. Primary Objective

The primary objective of this study is as follows:

 to assess the long-term safety of migalastat treatment in pediatric subjects diagnosed with Fabry disease and who have variants in the gene encoding α-Galactosidase A (*GLA*) amenable to treatment with migalastat

2.1.2. Secondary Objectives

The secondary objectives of this study are as follows:

- to characterize the pharmacodynamics (PD) of migalastat in pediatric subjects diagnosed with Fabry disease and who have *GLA* variants amenable to treatment with migalastat
- to assess the efficacy of migalastat in pediatric subjects diagnosed with Fabry disease and who have *GLA* variants amenable to treatment with migalastat.

2.2. Study Endpoints

2.2.1. Efficacy Endpoints

The efficacy endpoints of this study are as follows:

- change from baseline in estimated glomerular filtration rate (eGFR; Schwartz formula)
- change from baseline in urine protein and albumin levels
- change from baseline in left ventricular mass index (LVMi)
- change from baseline in Fabry-Specific Pediatric Health and Pain Questionnaire (FPHPQ) scores
- change from baseline in Pediatric Quality of Life Inventory[™] (PedsQL[™])

2.2.2. Pharmacodynamic Endpoints

The PD endpoint of this study is the change from baseline in plasma levels of Globotriaosylsphingosine (lyso-Gb3).

2.2.3. Safety Endpoints

The safety endpoints of this study are as follows:

- incidence of treatment-emergent adverse events (TEAEs), serious adverse events (SAEs), and adverse events (AEs) leading to discontinuation of study drug
- change from baseline in clinical laboratory test results over time
- change from baseline in vital signs over time
- change from baseline in physical examination findings over time
- change from baseline in body weight and height over time
- change from baseline in electrocardiogram (ECG) results over time

- change from baseline in echocardiogram (ECHO) parameters from baseline to Month 12/ET
- change from baseline in Tanner stage

3. Study Design

3.1. Summary of Study Design

This is a long-term, open-label, uncontrolled, multicenter study to evaluate the safety, PD, and efficacy of migalastat treatment in subjects over 12 years of age with Fabry disease and with amenable GLA variants. Subjects will enroll in this study following completion of migalastat Study AT1001-020.

Enrollment in this study should immediately follow completion of Study AT1001-020 in order to maintain the continuity of treatment. As appropriate, assessments performed at the End of Treatment visit for Study AT1001-020 will be utilized for Visit 1 (baseline) assessments for this study.

In order to monitor safety, subsequent visits for this study were initially scheduled every 3 months with monthly interim telephone contacts. Following Amendment 2, the visit schedule was changed to every 6 months, with phone contacts at intervening 3-month intervals.

Subjects will remain on the same dose of migalastat that they were receiving in Study AT1001-020. If a subject's weight decreases to below 43 kg, an unscheduled visit will be arranged 2 to 4 weeks later in order to monitor the subject's weight.

3.2. Subject Selection

Inclusion and exclusion criteria for this study can be found in Section 8.2 of the study protocol. Waivers of inclusion/exclusion criteria will not be granted.

3.3. Determination of Sample Size

As this study is an open-label extension of Study AT1001-020, no sample size calculation was performed.

3.4. Treatment Assignment and Blinding

As this study is an open-label extension of Study AT1001-020 and all subjects receive migalastat, no treatment assignment is conducted, and no blinding process is used for this study.

3.5. Administration of Study Medication

Migalastat will be supplied as 150-mg capsules. Migalastat capsules contain 123 mg migalastat free base, which is equivalent to 150 mg migalastat HCI. Migalastat will be administered every other day (QOD) during the treatment period. Capsules are to be taken with water at the same time of day during the QOD dosing schedule. Subjects will be instructed not to eat for at least 2 hours before and for 2 hours after administration of study drug. Water can be consumed during this period.

Study drug should not be taken on 2 consecutive days. If a dose is missed entirely for the day, the subject should take the missed dose of study drug only if it is within 12 hours of the time the dose normally is taken. If more than 12 hours have passed, the subject should resume taking study drug at the next planned dosing day and time according to the every-other-day dosing schedule.

3.6. Study Procedures and Flowchart

Table 1 details the schedule of assessments:

Table 1. Schedule of Assessments

Assessments	Baseline ^a		Treatment Period					EOT/ ET	Follow- up		
Visit Interval	Day 1	Month 3 (TC)	Month 6	Month 9 (TC)	Month 12	Month 15 (TC)	Month 18	Month 21 (TC)	Month 24		30-Day Safety
Visit Window (days)	—	±6	±6	±6	±6	±6	±6	±6	±6	±6	±6
Informed consent/assent	х										
Inclusion/exclusion criteria	х										
Medical history	х										
Concomitant medications	х	Х	х	х	х	Х	Х	х	х	х	
Dosing diary ^b	х	\rightarrow	\rightarrow	\rightarrow	\rightarrow	\rightarrow	\rightarrow	\rightarrow	х		
FPHPQ questionnaire	х		х		Х		х		х	х	
PedsQL	х		х		Х		х		х	х	
Complete physical examination	х		х		Х		Х		Х	х	
Adverse events		Х	х	х	Х	х	Х	х	х	х	х
Vital signs (BP, HR, RR, Temp)	х		х		Х		Х		х	х	
Body weight	х		х		Х		х		х	х	
Height	Х		х		Х		Х		х	х	
Tanner Staging	х		х		Х		Х		х	х	
12-lead ECG	х		х		Х		Х		х	х	

Assessments	Baseline ^a		Treatment Period							EOT/ ET	Follow-up
Visit Interval	Day 1	Month 3 (TC)	Month 6	Month 9 (TC)	Month 12	Month 15 (TC)	Month 18	Month 21 (TC)	Month 24		30-Day Safety
Visit Window (days)	—	±6	±6	±6	±6	±6	±6	±6	±6	±6	+6
Chemistry (including eGFR using Schwartz formula)	х		х		Х		Х		Х	Х	
Hematology	х		х		х		х		х	х	
Plasma lyso-Gb ₃ , analogs, and exploratory PD biomarkers	Х		Х		х		х		х	Х	
Urinalysis (urine protein, albumin and microalbumin levels)	х		х		х		х		х	Х	
Urine pregnancy test or date of LMP (as applicable)°	х	х	Х	Х	Х	х	Х	х	Х	Х	X
Echocardiogram (LVMi and additional parameters)	х				Х				Х	Х	
Study treatment supply/resupply/ return	х		х		х		х		Х	Xd	

Table 1. Schedule of Assessments (Continued)

Abbreviations: BP = blood pressure; ECG = electrocardiogram; eGFR = estimated glomerular filtration rate; EOT = end of treatment; ET = early termination; FPHPQ = Fabry-Specific Pediatric Health and Pain Questionnaire; HR = heart rate; LMP = last menstrual period; LVMi = left ventricular mass index; lyso-Gb₃ = Globotriaosylsphingosine; PD = pharmacodynamic; PedsQL = Pediatric Quality of Life Inventory; RR = respiration rate; TC = telephone call; Temp = body temperature

Note: Following Month 24, visits will continue every 6 months with interim telephone contacts at 3-month intervals. The assessment schedule will repeat starting from Month 3. Note: For the purposes of this study, a month is considered to be 30 days.

^a End of study assessments from Study AT1001-020 will be used as baseline assessments for Study AT1001-036.

^b A dosing diary will be completed throughout the treatment period.

^o Female subjects only; urine pregnancy tests will be conducted at each site visit. For menstruating females, date of LMP will be elicited during telephone contacts.

^d Return of study drug only

4. Analysis Population

4.1. Enrolled Population

The enrolled population will include all enrolled subjects. All safety, PD, and efficacy analyses will be performed using the enrolled population.

4.2. Protocol Deviations

Protocol deviations are defined as instances in which subjects or investigational site study personnel fail to adhere to the protocol requirements (e.g., eligibility criteria, addition or deletion of tests, dosing, duration of treatment, and/or any other aspect of the study design). Deviations are collected on the electronic Case Report Forms (eCRF). Deviations related to the COVID-19 pandemic are indicated by including "COVID-19" in the deviation details field.

A list of protocol and site deviations will be provided with the date the deviation occurs, the category (eg, inclusion/exclusion criteria, informed consent (ICF)/subject privacy, etc.), and the description of the deviation.

5. General Aspects for Statistical Analysis

This section addresses the definitions, algorithms, imputations, and conventions that apply to the analysis and handling of the data.

5.1. General Summary Table and Individual Subject Data Listing Considerations

Summary tables and listings will have text (eg, headers or footers) providing explanatory notes that cover, as appropriate: date of data extraction, date of output generation, Statistical Analysis System (SAS®) program name, and any other output-specific details that require further elaboration.

The descriptive summary statistics will be prepared for baseline, each visit, and change from baseline to each visit (if appropriate).

Row entries in post text tables are made only if data exist for at least one subject (eg, a row with all zeroes will not appear). The only exception to this rule applies to tables that summarize the study termination status of subjects (eg, reasons for not completing the study). In this case, zeroes will appear for study termination reasons that no subject satisfied. The summary tables will clearly indicate the number of subjects to which the data apply and data that is unknown or not performed will be distinguished from missing data. All data collected will be reported in data listings.

Missing dates will be imputed as described in Section 5.7. Missing AE severity and relationship will be imputed as described in Section 5.7.2. No other missing data imputation will be performed. When imputed or derived data are included in the individual subject data listings, they will be flagged.

5.2. General Post Text Summary Table and Individual Subject Data Listing Format Considerations

The convention will be to number tables and listings using a decimal system to reflect main levels of unique tables and listings and sub-levels of replicate tables and listings. The first level number will be consistent with the corresponding CSR appendix in which the tables or listings will appear. Thus, all post text tables will have a main number level 14 and listings will have a main number level 16.

Subject accounting and final disposition, analysis populations, protocol deviations and/or violations, demographics and baseline profile will appear as the second level number (Table 14.1 series). Efficacy tables will come next (Table 14.2 series). Safety tables will be at the end (Table 14.3 series). Similar conventions will be applied to the subject data listings and figures/graphs.

For tables, the last line of the title will provide the analysis group being summarized (eg, Enrolled Population). Whether in the title or body of a table or listing, units will always be specified for all appropriate data. Metric system units will be used (eg, degrees Celsius [°C] for temperature, kg for body weight, and centimeters [cm] for height).

In general, the listings will be sorted and presented by investigational site and subject number. From left to right, the columns will include the subject number, visit number, visit name, visit date, treatment, and days relative to first dose in the study.

5.3. Data management

Datasets will be created according to Clinical Data Interchange Standards Consortium (CDISC) standards. The most current or latest version of the Study Data Tabulation Model (SDTM) datasets will be used. All statistical and data analyses, SDTMs and Analysis Data Model (ADaM) datasets will be created

using SAS[®] software version 9.4 or later. The data specifications and reviewer's guide will also be created.

5.4. Data Presentation Conventions

5.4.1. Descriptive Statistics

Data will be summarized with descriptive statistics and/or response frequencies. For numerical data, descriptive statistics will include number of subjects with non-missing data (n), mean, standard deviation (SD), median, minimum, and maximum. For categorical data, descriptive statistics will be categorized by frequency counts and proportions (or percentages) of the number of subjects used in the analysis. The counts for the categories of 'Missing,' 'Unknown,' or 'Not applicable' will be provided as appropriate, but the percentages will not be provided.

5.4.2. Rounding

In general, the minimum and maximum will be reported to the same number of decimal places as the data. The mean, median, and confidence intervals will be rounded to one more decimal place than the data. The SD will be rounded to two more decimal places than the data. Proportions will be reported as percentages rounded to one decimal place.

Each subject's age will be truncated to a whole number (rather than rounded).

5.4.3. p-values

Not applicable.

5.4.4. Dictionaries

The Medical Dictionary for Regulatory Activities (MedDRA, version 21.0 or later version) will be used to code AEs and medical history into system organ class (SOC) and preferred term (PT) within SOC. The enhanced version of the World Health Organization Drug Dictionary (WHO-DD, WHO Drug Enhanced + Herbal B3 March 2018, or latest available version) will be used to code all medications (prior and concomitant) to anatomical therapeutic chemical (ATC) class and preferred drug names.

5.5. Baseline Definition

For all safety, PD, and efficacy data, the baseline value is defined as the last non-missing measurement obtained on or before the administration of the first dose of study drug in Study AT1001-036 (Day 1).

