- change from baseline in Tanner Stage

Pharmacodynamic Assessments:

The primary PD biomarker to be evaluated in this study is lyso-Gb₃ levels in plasma. Exploratory evaluation of lyso-Gb₃ analogues and other potential Fabry biomarkers (non-genetic) also may be explored from these samples.

The PD endpoint is change from baseline in plasma levels of lyso-Gb₃.

Efficacy Assessments:

Efficacy assessments include eGFR, urine protein and albumin levels, left ventricular mass index (LVMi) and other cardiac parameters using echocardiograms, and subject questionnaires (Fabry-Specific Pediatric Health and Pain Questionnaire [FPHPQ], and Pediatric Quality of Life InventoryTM [PedsQLTM]).

Efficacy endpoints are as follows:

- change from baseline in eGFR (Schwartz formula)
- change from baseline in urine protein and albumin levels
- change from baseline in LVMi
- change from baseline in FPHPQ scores
- change from baseline in PedsQL scores

For analysis purposes, baseline value for efficacy endpoints for subjects enrolled in this study will be the baseline visit of Study AT1001-020.

Note: Estimated GFR will be calculated using the Schwartz formula throughout the study, regardless of the subject's age at the time of assessment. For subjects ≥ 18 years of age, the Schwartz formula will be applied by the sponsor at the time the value is entered into the database.

Statistical Methods:

The safety population will include all subjects who receive at least 1 dose or partial dose of study drug. All safety and PD analyses will be performed using the safety population.

The intent-to-treat population will include all enrolled subjects. All efficacy analyses will be performed using the intent-to-treat population.

Data will be summarized using descriptive statistics. Continuous variables will be summarized by number of subjects, mean, standard deviation, median, minimum, and maximum values. Discrete variables will be summarized by counts and percentages. In general, data will be summarized by age group at baseline, by sex, and combined across all subjects.

3.	TABLE OF CONTENTS AND LIST OF TABLES
	TABLE OF CONTENTS

1.	DECLARATIONS OF SPONSOR AND INVESTIGATOR	3
1.1.	Declaration of Sponsor	3
1.2.	Declaration of Investigator	3
2.	SYNOPSIS	4
3.	TABLE OF CONTENTS AND LIST OF TABLES	8
4.	LIST OF ABBREVIATIONS AND DEFINITIONS OF TERMS	13
5.	INTRODUCTION AND STUDY RATIONALE	14
5.1.	Fabry Disease	14
5.2.	Migalastat	15
5.3.	Summary of Nonclinical and Clinical Safety Data	15

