11.4. Statistical Methods

For the purpose of statistical analyses, baseline is generally defined as the last non missing measurement obtained on or before the administration of the first dose of study drug. For this study, the baseline value for efficacy endpoints will be obtained from the baseline visit of Study AT1001-020.

Only summary statistics will be provided for data collected from this study. No missing data imputation method is planned to handle missing data. Data will be summarized as observed.

Data will be summarized using descriptive statistics. Continuous variables will be summarized by number of subjects, mean, standard deviation, median, minimum, and maximum values. Discrete variables will be summarized by counts and percentages.

In general, data will be summarized by age group at baseline, by sex, and combined across all subjects.

A month will be defined as 30 days.

No missing data imputation method is planned to handle missing data. Data will be summarized as observed. All data will be listed.

Full details will be presented in the SAP.

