This SAP is created based on Protocol AT1001-036, Amendment 2, 19Aug2021. The purpose of this SAP is to outline the planned analyses by Syneos Health to support the completion of the Clinical Study Report (CSR). This SAP describes in detail the statistical methodology and the statistical analyses to be conducted for the above-mentioned protocol. The planned analyses identified in this SAP are following the International Council for Harmonisation of Technical Requirements for Pharmaceuticals for Human Use (ICH) guidelines E9 (R1) Statistical Principles for Clinical Trials. They will be included in regulatory submissions and/or future manuscripts.

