5.6.1.2. Study Day

Study Day 1 denotes the day of the first dose of study drug in Study AT1001-036 and is the reference start date for all analyses in this study. Study days (or visit days) are defined relative to Day 1 unless otherwise specified. Days prior to Day 1 are negative and days after Day 1 are positive. There is no Day 0. That is,

Relative Day = (Date of Assessment) – (Date of First Dose of Study Drug) + 1, if assessment is on or after the date of first dose of study drug;

Relative Day = (Date of Assessment) – (Date of First Dose of Study Drug), if assessment is before the date of first dose of study drug.

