9.7. Tanner Stage

A summary table of assessment results in Tanner stage will be provided at each scheduled visit by sex (male, female), ERT status (ERT naïve, ERT experienced), and overall if feasible for the enrolled population. By-visit summary will also include the last post-baseline values.

A by-subject listing will be presented for each Tanner stage parameter, including pubic hair development, breast development, and genital development.

10. Reference List

Online source for PedsQL[™] scoring:

http://www.lsebn.nhs.uk/website/X13911/files/20%20scoring_PedsQL_v13[1].pdf

11. Interim Analyses

No interim analyses are planned.

12. Changes from Analysis Planned in Protocol

As the subjects who receive at least 1 dose or partial dose of study drug will coincide with enrolled subjects in this study, the safety and intent-to-treat population have been removed and replaced with a single "enrolled population. All PD and safety analyses will be conducted on the enrolled population.

No other changes are planned from the analyses described in the protocol amendment 1 (24JUN2019),

13. Programming Considerations

All TLFs and statistical analyses will be generated using SAS[®] for Windows, Release 9.4 (SAS[®] Institute Inc., Cary, NC, USA). Computer-generated table, listing and figure output will adhere to the following specifications.

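### The SAP measures efficacy change from AT1001-036 Day 1, when subjects are already on migalastat, instead of the protocol's AT1001-020 baseline, and does not declare the change

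*SAP*

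**What the plan says.** Protocol Section 11.4 opens with a general rule: "baseline is generally defined as the last non missing measurement obtained on or before the administration of the first dose of study drug". The next sentence makes an exception: "For this study, the baseline value for efficacy endpoints will be obtained from the baseline visit of Study AT1001-020". The Synopsis repeats it under the efficacy endpoints: "baseline value for efficacy endpoints for subjects enrolled in this study will be the baseline visit of Study AT1001-020".

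SAP 5.5 has no exception: "For all safety, PD, and efficacy data, the baseline value is defined as the last non-missing measurement obtained on or before the administration". The rest of that sentence ties the rule to the extension study by naming the "first dose of study drug in Study AT1001-036 (Day 1"). SAP 5.6.1.2 adds that Study Day 1 "is the reference start date for all analyses in this study", and SAP 5.6.1.4 computes change by subtracting the baseline so defined. No other SAP section brings back an AT1001-020 baseline for efficacy.

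SAP Section 12 declares one departure from the protocol, the merging of the safety and intent-to-treat populations into an enrolled population. It then states: "No other changes are planned from the analyses described in the protocol amendment 1 (24JUN2019"). The SAP Introduction names a later version as its basis: "This SAP is created based on Protocol AT1001-036, Amendment 2, 19Aug2021".

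**The concern.** AT1001-036 is an extension study. Subjects keep the dose they had in AT1001-020, the protocol intends uninterrupted treatment (Sections 7.1 and 9.1.2), and the end-of-study assessments of AT1001-020 serve as the AT1001-036 baseline assessments (footnote a to the schedule in both documents). The SAP baseline is therefore an on-treatment value for anyone who rolls over as planned, whereas the protocol's efficacy baseline is the starting point of the parent study.

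The analysis is descriptive only, so the change tables and the mean plots of SAP Section 7 are the main efficacy result, and their reference point decides what they show. Under SAP 5.5, change in eGFR, urine protein and albumin, LVMi, FPHPQ and PedsQL covers only the period after AT1001-020. An improvement or a decline during that study would not appear in any change summary. A reader who relies on Section 12 would assume that the changes are measured from the protocol's baseline.

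**Working it through.** The documents contain no figure to reproduce: there is no sample size calculation, no test and no assumed effect. The check compares the definitions and then works through the change formula.

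**Definitions side by side**

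| Data | Protocol | SAP 5.5 |
|---|---|---|
| Safety, PD | General rule: latest value up to first dose | Latest value up to first AT1001-036 dose |
| Efficacy | Baseline visit of AT1001-020 | Latest value up to first AT1001-036 dose |

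The documents conflict in the efficacy row only.

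**What the formula drops.** Let B20 be a subject's value at the AT1001-020 baseline visit, B36 the value at AT1001-036 Day 1, and Yt the value at visit t.

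- Protocol change = Yt − B20
- SAP change = Yt − B36
- Protocol change = SAP change + (B36 − B20)

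The SAP result omits B36 − B20 for every subject at every visit. Among subjects with all three values, the two mean changes differ by the mean of B36 − B20. This holds for all five efficacy endpoints, since each is a change from baseline.

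**Illustrative size.** The documents give no values for B36 − B20 and do not state how long AT1001-020 lasted. Assume a duration T of 0.5 to 1 year, change at a constant rate from the AT1001-020 baseline onward, and Month 12 and Month 24 as t = 1 and t = 2 years. The share of the accumulated change missing from the SAP result is T/(t + T):

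| | t = 1 (Month 12) | t = 2 (Month 24) |
|---|---|---|
| T = 0.5 | 0.5/1.5 = 33% | 0.5/2.5 = 20% |
| T = 1 | 1/2 = 50% | 1/3 = 33% |

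If an endpoint instead changes during AT1001-020 and then stays level, Yt = B36. The SAP change is then 0 and the protocol change is B36 − B20, so 100% is missing.

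**Is the departure declared?** Section 12 lists only the population change. Against Amendment 2, the SAP's stated basis, the baseline change is undeclared. The text of Amendment 1 is not available, so whether the sentence is accurate for the version it cites cannot be judged.

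**The case against.** The study's primary objective is long-term safety, which this conflict does not touch. Efficacy is secondary and descriptive, so no test or error rate is affected. SAP 5.5 states its anchor openly, and observed values are summarised at baseline and at each visit, so absolute levels within AT1001-036 stay visible. The protocol itself uses the word baseline in two senses: footnote a to Table 2 lets AT1001-020 end-of-study assessments fill Visit 1, and Section 11.4 begins with a last-value-before-dose rule. The SAP may simply have applied that general rule. The percentages depend on an assumed duration and trajectory. Finally, without a control arm, B36 − B20 mixes drug effect, growth and disease course.

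Much of this stands as a limit on wording. The omitted term should be described as change accrued during AT1001-020, not as drug effect, and the percentages are illustrations only. The conflict itself remains. The footnote says which visit supplies the Visit 1 procedures; Section 11.4 and the Synopsis say which value is the analysis baseline for efficacy. The protocol satisfies both statements and SAP 5.5 satisfies only the first. The observed-value tables do not help, because their baseline row is Day 1 and the AT1001-020 starting value appears nowhere. Naming Day 1 in Section 5.5 also does not tell a reader that the protocol specified something else.

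**Conclusion.** The concern holds. SAP 5.5 contradicts the protocol on the baseline for all five efficacy endpoints, and Section 12 does not declare it against Amendment 2. Followed as written, the SAP removes B36 − B20 from every efficacy change. That result is exact and needs no assumption. The actual size and direction cannot be computed from the documents; the range of 20% to 50% rests on the assumed 0.5 to 1 year and a constant rate, and the 100% case on a plateau.

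A few subjects may be off drug at Day 1 (a gap of more than 30 days, or approved entry after withdrawing from AT1001-020), but the algebra is the same for them. The conflict does not extend to safety or PD, for which the protocol makes no AT1001-020 exception. It should be corrected before the analysis is run, because the rule is wrong as written and not merely incomplete.

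**What to change.** 1. Rewrite SAP 5.5 with two definitions: for efficacy endpoints, the AT1001-020 baseline visit, as in the protocol; for safety and PD, the latest value up to the first AT1001-036 dose. Day 1 can remain the reference for study-day numbering in 5.6.1.2.
2. State in each table title or footnote which baseline applies. This matters for eGFR, urine protein and urine albumin, which appear in the efficacy summaries (SAP 7.1) and in the safety shift tables (SAP 9.3), and for echocardiogram parameters, which the protocol lists under both safety and efficacy.
3. Bring the AT1001-020 baseline efficacy records into the analysis datasets, and confirm that the imported eGFR uses the same Schwartz version as SAP 7.1.
4. Show efficacy change from AT1001-036 Day 1 as a supplementary column. A column for lyso-Gb3 change from the AT1001-020 baseline would be useful, but the protocol does not require it.
5. Correct Section 12 so that it compares with Amendment 2. If the sponsor prefers Day 1 as the main efficacy baseline, list that there with a reason and report the protocol baseline as well.

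The cost is SAP wording, one import and one extra set of change columns. The SAP already takes birth date and ERT status from AT1001-020, and the protocol takes demographics from that study's baseline visit. That the efficacy baseline values are equally to hand is a reasonable assumption, though not stated. No new data collection in AT1001-036 is involved.
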